5 PARTICIPANT SELECTION

5.1 Inclusion Criteria

To be included in this study, participants must meet the following criteria:

- 1. Age \geq 18 years of age.
- 2. Have a Karnofsky performance status ≥ 70 (i.e. the patient must be able to care for himself/ herself with occasional help from others; refer to **Appendix B**).
- 3. Documented survivin-positive tumor status.
- 4. Pathologically confirmed diagnosis of glioblastoma multiforme (GBM). Or WHO grade IV [gliosarcoma]
- 5. Have the following clinical laboratory values obtained within 14 days prior to registration:
 - Absolute neutrophil count (ANC) $\geq 1.5 \times 10^9/L$
 - Platelets $> 100 \times 10^9/L$
 - Hemoglobin (Hgb) > 9.0 g/dL
 - Serum total bilirubin: $\leq 1.5 \text{ x ULN}$
 - ALT and AST < 4.0 x ULN
- 6. Patients on full-dose anticoagulants (e.g., warfarin or LMW heparin) must meet the following criteria:
 - No active bleeding or pathological condition that carries a high risk of bleeding (e.g., tumor involving major vessels or known varices)
- 7. Adequate renal function, as defined below:
 - Creatinine $\leq 1.8 \text{ mg/dl}$
- 8. HLA-A*02, HLA-A*03, HLA-A*11 or HLA-A*24 positive patients.
- 9. MRI (completed within 96 hours after surgery) documenting gross total resection consisting of no gadolinium enhancement; or subtotal resection consisting of linear enhancement with (or without) nodular gadolinium enhancement measuring no greater than 1 cm x 1 cm x 1 cm total volume or 100 mm² in cross sectional area.
- 10. No evidence of true progressive disease from the postoperative period to the post-chemoradiation period, based on changes in the neurologic exam, steroid use, or evident radiographic progression, according to RANO criteria (see **Appendix C**). Patients with increased or new gadolinium enhancement may continue on protocol if in the investigator's judgment that enhancement is likely due to pseuodoprogression. The use of correlative imaging studies (including PWI) or diffusion weighted imaging (DWI), and

- repeat imaging after an interval of 2-4 weeks is strongly encouraged to help distinguish between pseudoprogression and true progression.

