9.2 Evaluation of Response

The largest cross-sectional area on the T1-weighted contrast-enhanced images will be selected and measured in 2 dimensions with linear measures on the baseline MRI axial sequence. In addition, the largest cross-sectional area of a contiguous hyperintense lesion on FLAIR sequences will be measured on the baseline MRI axial sequence. If there is no enhancement on the baseline MRI done with 72 hours post-op, this should be noted as no evidence of disease (NED). All subsequent scans will be compared against these baseline measures (for both CE and FLAIR). New foci of FLAIR signal abnormality will be recorded on each subsequent evaluation. Response will be scored based on a combination of imaging and clinical features as defined by the modified RANO criteria (40). Objective response rate is defined as the sum of partial responses plus complete responses.

For the purpose of treatment decisions, progression will be assessed by the treating investigator. 20% to 30% of patients who receive chemoradiotherapy for newly diagnosed glioblastoma can exhibit transient increase in tumor enhancement that eventually subsides without change in therapy (pseudoprogression) (40). The protocol allows for investigators to confirm progression before removal of patients from study treatment, thus ensuring radiographic follow-up to a valid disease progression time point. In every case when there is doubt about progression versus "pseudoprogression", use of perfusion and diffusion weighted imaging is encouraged. Patients may continue on treatment and remain under close observation and evaluation at four-week intervals if there is uncertainty regarding whether apparent radiographic progression may represent "pseudoprogression" and the patient is doing well clinically or is clinically stable. If subsequent evaluations indicate that the patient is in fact experiencing progression, then the date of progression should be the time point at which this issue was first raised.

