9.2.1 Survival

Duration of survival will be defined as the time from date of diagnosis to death due to any cause.

In all cases, progression-free survival will be assessed using the RANO response criteria for GBM which considers radiologic imaging, neurological status, and steroid dosing. According to these criteria, progression of disease will be assumed if any of the following criteria are met:

• ≥25% increase in the sum of the products of perpendicular diameters of enhancing lesions compared with baseline (post-chemoradiation) or best response after initiation of therapy.

NOTE: Due to the fact that little to no residual disease will be present at baseline in these patients, a 25% increase in area could easily reflect only imaging variance. Therefore, in order to be considered progressive disease, a > 5 mm increase in maximal diameter, as well as $\ge 25\%$

increase in the sum of the products of the progressing lesions will be required to assign a status of progressive disease.

- Significant increase in T2/FLAIR non-enhancing lesion compared with baseline (post-chemoradiation) or best response after initiation of therapy, not caused by comorbid events (e.g., radiation therapy, demyelination, ischemic injury, infection, seizures, postoperative changes, or other treatment effects).
- Clear progression of non-measurable disease.
- Any new lesion.

NOTE: Patients may continue on treatment and remain under close observation and evaluation at four-week intervals if there is uncertainty regarding whether apparent radiographic progression may represent "pseudoprogression". If subsequent evaluations suggest that the patient is in fact experiencing progression, then the date of progression should be the time point at which this issue was first raised. Similarly, stable disease may be assigned in cases of presumed "pseudoprogression" associated with decreased steroid use.

- Clear clinical deterioration not attributable to other causes apart from the tumor (e.g., seizures, medication adverse effects, complications of therapy, cerebrovascular events, infection, and so on) or changes in corticosteroid dose
- Failure to return for evaluation as a result of death or deteriorating condition

NOTE: Any cystic or surgical cavity should not be measured in determining response. At baseline, tumor around the surgical cavity should generally be considered nonmeasurable unless there is a nodular component measuring 10 mm in diameter.

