Both objective tumor response rate (applicable only for patients with evaluable disease at study entry, as defined per RANO criteria) and toxicity rate (Grade 3 or Grade 4 toxicities, according to National Cancer Institute Common Toxicity Criteria for Adverse Events (NCI CTCAEs) Version 4) will be estimated using simple relative frequencies. The corresponding 95% confidence intervals for the estimated probabilities will be computed using the method proposed in Clopper and Pearson, 1934 ⁽⁴³⁾. The relationship between binary outcomes and collected demographic and baseline variables will be statistically assessed using logistic regression in an exploratory fashion. Maximum likelihood estimation will be utilized in the model fitting procedures as implemented by SAS PROC LOGISTIC. Wald tests of the model effects will be performed to assess statistical significance; see SAS documentation for details. See Hosmer and Lemeshow, 2000 ⁽⁴⁴⁾ for a discussion of such techniques. Alternative parametric models will be considered if model fit is found to be inadequate.

Objectives based on continuous outcomes such as immune response measured over time will be address in a similar fashion. A series of exploratory analyses will initially take place including individual subject-level profile plots and overall mean plots used to examining the mean structure. Formal statistical examination of longitudinal patterns will be done through the use of

a mixed model. Restricted maximum likelihood estimation will be utilized in the model fitting procedures as implemented by SAS PROC MIXED (version 9.2). Once the model is fit, specific linear contrasts based on the estimated model parameters will be constructed and used to test hypotheses concerning between time point comparisons. We acknowledge the possibility of informative missingness, that is, the probability of a particular observation being missing may be related to the health of the subject, and therefore analyses will be interpreted with caution.

All tests will be two-sided and tested at a 0.05 nominal significance level. Standard diagnostic plots will be used to assess model fit and transformations of variables may be considered in order to meet statistical assumptions.

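### The objective response rate could count spontaneous resolution of presumed pseudoprogression as response, because neither the response baseline scan nor the evaluable population is fixed

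*Combined protocol and SAP*

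**What the plan says.** All references are to the combined protocol and SAP.

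- **Endpoint.** Section 9.2: "Objective response rate is defined as the sum of partial responses plus complete responses". Section 12.7.1 (Secondary Analyses) gives the population: "Both objective tumor response rate (applicable only for patients with evaluable disease at study entry, as defined per RANO criteria". It adds a Clopper-Pearson 95% interval and exploratory logistic models for predictors. Sections 3.2 and 12.2 list the rate and its predictors as a secondary objective.
- **Residual tumour allowed at entry.** Section 5.1 item 9 accepts gross total resection, or subtotal resection with "nodular gadolinium enhancement measuring no greater than 1 cm x 1 cm x 1 cm total volume", or 100 mm² in cross section.
- **Measurability.** Section 9.2.1: "tumor around the surgical cavity should generally be considered nonmeasurable unless there is a nodular component measuring 10 mm in diameter". The same section expects that "little to no residual disease will be present at baseline in these patients".
- **Pseudoprogression allowed at entry.** Section 5.1 item 10: "Patients with increased or new gadolinium enhancement may continue on protocol", if the investigator thinks pseudoprogression the likely cause. No size limit is attached.
- **Its natural course.** Section 9.2 says that 20% to 30% of chemoradiated patients "can exhibit transient increase in tumor enhancement that eventually subsides without change in therapy (pseudoprogression").
- **Baseline scan.** Section 9.2 takes its baseline measures from the post-operative MRI and compares all later scans with them. Section 9.2.1, in its progression criteria, names the post-chemoradiation scan as baseline. Appendix C does not say which scan is meant.

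**The concern.** The rules for who enters, who is evaluable and which scan is the reference do not fit together. True residual tumour large enough to measure is nearly excluded by item 9. The one kind of enhancement that item 10 admits without a size limit is the kind that the protocol expects to disappear by itself. Nothing in Sections 9.2 or 12.7.1 takes those patients out of the response rate, and there is no control arm to show how much shrinkage would have occurred anyway.

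At stake is what the response rate means. It could describe the course of radiation-related enhancement, or shrinkage caused by chemoradiation, rather than change after SurVaxM begins. The predictor models could then identify predictors of pseudoprogression resolving. A reader planning the next trial could take a high rate from a single arm as activity.

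**Working it through.** **1. The plan's own figures.** The plan gives no expected response rate, denominator or precision. Its only sample size is for PFS6 (Section 12.4: null 0.55, alternative 0.70, one-sided alpha 0.10, power 0.80, exact test, n=50). That reproduces closely: at n=50 the test rejects at 33 or more successes, with exact alpha 0.0765 and power 0.782. The smallest n with at least 80% exact power is 49 (32 or more, alpha 0.0948, power 0.810). The response rate does not enter this calculation.

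**2. Entry cap against measurability threshold.** The cap is 10 mm × 10 mm = 100 mm² in cross section, and the threshold is a 10 mm nodule. A residual nodule can be both eligible and measurable only at the limit, or if it is elongated within the area alternative (for example 20 mm × 5 mm = 100 mm²). So there is little such tumour, though not necessarily none.

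**3. What each baseline does.**

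| Response baseline | Pseudoprogression on the entry scan | Other consequence |
|---|---|---|
| Post-chemoradiation (as in 9.2.1) | Is part of the baseline. A fall of more than 50% held for 4 weeks, or full clearance, can meet Appendix C for PR or CR | Change is measured from about the start of vaccination |
| Post-operative (as in 9.2) | Is not in the baseline, so its disappearance is not a PR. The patient can still be in the denominator, which is chosen on disease at study entry | Shrinkage of true residual tumour during chemoradiation, before the first vaccine dose, can count as response |

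For the second row, Section 4.1 gives about 4 weeks of recovery, 6 weeks of chemoradiation and a first dose 7–28 days later: 4 + 6 + 1 = 11 to 4 + 6 + 4 = 14 weeks between surgery and the first dose. Appendix C's steroid, FLAIR and neurological conditions, and its 4-week duration, do not separate resolving pseudoprogression from tumour response.

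**4. Illustration, post-chemoradiation baseline, no treatment effect.** From the plan: 0.20 × 50 = 10 and 0.30 × 50 = 15 patients with pseudoprogression. Assumptions that are not in the plan: all of them have evaluable enhancement on the entry scan; 50–100% shrink enough for PR or CR; 0–10 further patients have true measurable residual tumour and none of these respond.

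| Pseudoprogression | Residual | Shrinking | Apparent rate | Clopper-Pearson 95% |
|---|---|---|---|---|
| 10 | 10 | 5 | 5/20 = 25% | 9–49% |
| 10 | 5 | 8 | 8/15 = 53% | 27–79% |
| 15 | 0 | 15 | 15/15 = 100% | 78–100% |

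With the pseudoprogression patients removed, the same scenarios give 0% wherever a denominator remains. The upper limit is 52% for 0/5 and 31% for 0/10.

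**5. Illustration, post-operative baseline.** With 10 pseudoprogression and 5 residual-tumour patients in the denominator, and pseudoprogression scored as non-response, the rate cannot exceed 5/15 = 33%, even if all 5 residual tumours respond.

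**The case against.** The strongest reply is that the section defining the response rate uses the post-operative MRI. Pseudoprogression arises after that scan, so its disappearance only returns the patient to baseline, and a patient recorded as free of disease has nothing to shrink. The post-chemoradiation baseline in Section 9.2.1 is attached to progression. This stands in part: a reader might infer that the plan *would* score resolving pseudoprogression as response, and the documents do not establish that. It does not rescue the endpoint. The denominator is still chosen at study entry. Appendix C's CR asks for no residual enhancement without naming a reference scan. The post-operative baseline also brings in shrinkage from chemoradiation.

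Section 9.2.1 also lets investigators assign stable disease in presumed pseudoprogression. That label is optional, tied to reduced steroid use, and does not bar a later PR or CR.

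A reader might further infer that almost every evaluable patient is a pseudoprogression patient. The documents do not show this. *Evaluable* is not defined in the protocol and may be wider than *measurable*, elongated nodules can qualify, and pseudoprogression on the entry scan need not be measurable. The 20–30% describes all chemoradiated patients, not those enrolled.

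Finally, the impact is limited. Section 12.3 does not list the response rate among the endpoints, no target or decision rule depends on it, and the predictor models are already called exploratory. All of this stands, and it limits the weight of the point.

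**Conclusion.** The concern holds in conditional form. The response rate *could* count spontaneous resolution of presumed pseudoprogression as response, because Sections 9.2 and 9.2.1 name different baselines, *evaluable* is undefined and these patients are not excluded. Neither baseline, as written, isolates change after vaccination begins: one can credit resolving pseudoprogression, while the other can credit chemoradiation and dilute the denominator.

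The size is unknown. The apparent rates of 25% to 100% without any treatment effect show only how far the endpoint can move under a post-chemoradiation baseline and the stated assumptions. They are not a forecast. The point is confined to a secondary objective and does not touch PFS6 or n=50. It is still worth correcting, because the correction is cheap and a single-arm response rate is easily over-read.

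**What to change.** Amend Sections 3.2, 9.2, 12.2 and 12.7 as follows.

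1. Reconcile Sections 9.2 and 9.2.1 by naming one response baseline: an MRI after chemoradiation and before the first vaccine dose.
2. Define *evaluable* for objective response as a measurable nodule that was already present on the post-operative MRI and had not enlarged on the post-chemoradiation MRI.
3. Exclude patients whose entry enhancement was judged to be pseudoprogression from the response rate and its predictor models. Report their change in enhancement separately, as description. This needs a per-patient record, made before response is scored, that entry relied on the item 10 allowance.
4. State that few or no evaluable patients are expected, so the rate and its interval are descriptive.

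The cost is protocol and SAP wording, using scans already required. The price is a very small denominator, possibly zero, in which case the plan should say that no rate will be reported.

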12 STATISTICAL METHODOLOGY

12.1 Study Design

This is a multi-center, open-label; prospective one-arm phase II clinical trial evaluating the safety and efficacy of SurVaxM and adjuvant temozolomide in adult patients with newly diagnosed GBM. The statistical design is based on an assessment of the efficacy of the study treatment for patients as compared to an external standard, i.e., historical control. All enrolled patients will receive the study treatment and initiation of the treatment should take place as soon as possible following study enrollment. A total of up to 65 patients will be enrolled to meet our target of at least 50 evaluable patients. An evaluable subject is defined as a subject who meets eligibility requirements and who completes the initial four priming doses of the vaccine. If a patient signs an Informed Consent and does not receive all four priming injections or, the patient withdraws their consent before receiving the priming injections, the patient will be classified as unevaluable and will be replaced. Analyses will be performed with a focus on estimation of specific clinically important parameters for use in the planning of larger subsequent comparative trials designed to fully assess efficacy and safety.

All analyses will be performed using the SAS® statistical software system.

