12.2 Study Objectives

The primary objective of this study is:

• To evaluate 6 month progression-free survival (PFS) rates in patients with survivin positive newly diagnosed GBM treated with SurVaxM and adjuvant temozolomide.

The secondary objectives of this study are:

- To determine the safety and tolerability of SurVaxM in patients receiving standard of care temozolomide.
- To evaluate overall survival (OS) in patients with survivin positive newly diagnosed GBM treated with SurVaxM and adjuvant temozolomide.
- To describe the immune response in patients treated with SurVaxM and predictors of response.
- To evaluate objective tumor response rate (applicable only for patients with evaluable disease at study entry, as defined per RANO criteria) and predictors of response.

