12.4 Sample Size Determination

The primary endpoint will be the 6 month PFS survival fraction. Let π represent the 6 month PFS survival fraction. A true rate of the 6 month PFS survival fraction greater than π_0 =0.55 is considered acceptable and evidence such that we will the treatment worthy of further study. The null and alternative hypotheses to be tested are H_0 : π = π_0 versus H_a : π > π_0 . We hypothesize that patients treated with SurVaxM and adjuvant temozolomide will have a 6 month PFS survival fraction of 0.70 or larger. The sample size calculation is based on testing the hypotheses concerning the proportion of the population with a response to the treatment: H_0 : π = π_0 versus H_a : π > π_0 . For our calculations π_0 =0.55, α =0.10, 1- β =0.80. Based on an exact one-sided test the sample size calculation yields n=50 patients.

Subjects will be accrued to the study on a first-come basis. The projected accrual is approximately 2 subjects per month, and therefore recruitment is expected to be complete at 25 months following the study starting point. Subjects will be followed to determine time to tumor progression (PFS) and until death to determine overall survival (OS).

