12.8 Adverse Event

AEs will be coded using the latest available version of the Medical Dictionary for Regulatory Activities (MedDRA). AEs will be summarized for each treatment arm by the number and percentage of patients who experienced the event, according to system organ class and preferred term. Additional summaries will also be provided by severity grade and relationship to study drug, and for SAEs and events resulting in the permanent discontinuation of therapy. A patient reporting multiple cases of the same AE will be counted once within each system organ class and similarly counted once within each preferred term, and adverse events will be graded by worst severity grade. Unless specified otherwise, the denominator for these calculations will be based on the number of patients in each treatment arm who receive at least one dose of study drug, irrespective of the total number of doses administered. All participants who receive any study treatment will be considered evaluable for toxicity.

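### For sparse binary outcomes, the Wald test planned for predictor models breaks down when a covariate level has no events or only events; penalised-likelihood tests avoid this at little cost

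*Combined protocol and SAP*

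**What the plan says.** The secondary analyses in Section 12.7.1 estimate objective response and Grade 3-4 toxicity as simple proportions with Clopper-Pearson intervals. Binary outcomes are then related to demographic and baseline variables by logistic regression, described as exploratory and fitted by maximum likelihood in SAS PROC LOGISTIC. The only test named is this: "Wald tests of the model effects will be performed to assess statistical significance". Tests are two-sided at 0.05. If the model fits poorly, other parametric models may be considered. Nothing is said about separation, sparse cells or how many predictors may enter.

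The analysis serves a listed objective. Section 12.2 includes objective response "as defined per RANO criteria) and predictors of response" among the secondary objectives.

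The denominators differ by outcome:
- **Design:** "A total of up to 65 patients will be enrolled to meet our target of at least 50 evaluable patients" (Section 12.1).
- **Toxicity:** "All participants who receive any study treatment will be considered evaluable for toxicity" (Section 12.8), so possibly more than 50.
- **Response:** "Both objective tumor response rate (applicable only for patients with evaluable disease at study entry" (Section 12.7.1). The size of this subset is not given. Section 5.1 admits only patients with complete resection or minimal residual enhancement, and Section 9.2.1 expects hardly any residual tumour at baseline.

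**The concern.** The Wald statistic divides the estimated log odds ratio by its standard error. When every patient at one covariate level has the same outcome, the maximum-likelihood estimate does not exist. The fitted value runs off to infinity, its standard error grows faster, and the p-value drifts towards 1. The test therefore fails in some of the tables where the association looks strongest.

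At stake is whether the trial can answer its own question about predictors of tumour response, and whether the odds ratios it reports are usable. Section 12.1 says the analyses are meant to estimate quantities for planning larger comparative trials. An infinite odds ratio with a p-value near 1 does not help with that. If no remedy is written down, the method would be chosen after the problem appeared in the data.

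**Working it through.** **The plan's own figure.** The only sample-size figure belongs to the primary test: "For our calculations π_0 =0.55, α =0.10, 1- β =0.80", with patients expected to do as follows: "will have a 6 month PFS survival fraction of 0.70 or larger". The stated result is "Based on an exact one-sided test the sample size calculation yields n=50 patients". For n = 50 the exact rule is at least 33 successes, with one-sided error 0.0765 and power 0.782. For n = 49 the rule is at least 32, with error 0.0948 and power 0.810. So 50 is reproduced to within two patients and two percentage points. It has no bearing on the predictor models, for which no power or event count is stated.

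**Inputs.** From the plan: maximum likelihood, Wald test, two-sided 0.05, at least 50 evaluable and up to 65 enrolled. Assumed, because the documents give none: one binary predictor, the split between its levels, and the event rates.

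**Method.** All 2x2 tables (a of n1, b of n2) were enumerated with their binomial probabilities.
- *Wald:* z = ln[a(n2−b) / (b(n1−a))] / √(1/a + 1/b + 1/(n1−a) + 1/(n2−b)). Tables with an empty cell count as non-significant.
- *Firth:* the log-likelihood plus half the log determinant of the information. For a 2x2 table this gives p1 = (a+½)/(n1+1), p2 = (b+½)/(n2+1) and, under no association, p0 = (a+b+1)/(n1+n2+2). Twice the difference in penalised log-likelihood is referred to chi-square on 1 df.

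**One table, 6/25 v 0/25.** The maximum-likelihood odds ratio is infinite. Firth gives p1 = 6.5/26 = 0.250, p2 = 0.5/26 = 0.019, p0 = 7/52 = 0.135, and an odds ratio of (6.5 × 25.5)/(19.5 × 0.5) = 17. The penalised log-likelihoods (common constant dropped) are −17.09 and −20.54. The statistic is 2 × 3.45 = 6.90 and p = 0.009. Fisher's exact test gives 0.022.

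**How often a cell is empty.** With 25 per group and 30% v 5%, the low-rate group has no events with probability 0.95^25 = 0.28. With 30% v 3% it is 0.97^25 = 0.47. With 10 per group and 40% v 5% it is 0.95^10 = 0.60. The Wald test cannot reject in any of those tables.

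**Power at two-sided 0.05.**

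| Patients per group | Rates | Wald | Firth penalised LR |
|---|---|---|---|
| 25 / 25 | 30% v 3% | 0.31 | 0.82 |
| 25 / 25 | 30% v 5% | 0.37 | 0.70 |
| 25 / 25 | 30% v 10% | 0.32 | 0.42 |
| 25 / 25 | 55% v 20% | 0.75 | 0.75 |
| 25 / 25 | 70% v 30% | 0.81 | 0.81 |
| 32 / 33 | 30% v 5% | 0.59 | 0.80 |
| 10 / 10 | 40% v 5% | 0.06 | 0.43 |
| 10 / 10 | 50% v 10% | 0.18 | 0.47 |
| 10 / 10 | 70% v 30% | 0.36 | 0.42 |

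**Type I error of the Firth test**, for common rates of 5%, 10%, 20%, 30% and 50%: 0.020 to 0.049 at 25/25, 0.001 to 0.042 at 10/10, and 0.003 to 0.057 at 8/12. It stays below 0.05 in the balanced cases and goes slightly above it in the small unbalanced one. The Wald test at 25/25 rejects 0.5% of the time when the common rate is 10%.

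**Wald tests on Firth estimates** keep much of the loss: 0.46 instead of 0.70 (25/25, 30% v 5%) and 0.15 instead of 0.43 (10/10, 40% v 5%).

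**Four covariates** (simulation, 1,000 replicates per scenario), Wald v Firth: n = 50 with about 9 events, 0.56 v 0.82; n = 50 with about 23 events, 0.78 v 0.78; n = 20 with about 4 events, 0.02 v 0.30.

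**The case against.** The strongest reply is that sparsity is assumed. The plan gives no event counts, and the toxicity endpoint counts any Grade 3 or 4 event. Section 1.4.4 lists several haematologic abnormalities of that grade on temozolomide, each at 10% or more, so pooled toxicity may be common. If six-month PFS were modelled this way, the plan's own 0.70 and 0.55 imply 50 × 0.30 = 15 to 50 × 0.45 = 22.5 failures, which is not few. This stands, and it limits the point to outcomes that prove sparse.

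A reader might infer that the planned tests lose most of their power across all predictor analyses in about 50 patients. The documents do not support that. At moderate rates with 25 per group the gap is 0 to 2 points, and even at 30% v 5% the Wald test keeps over half of the Firth power. Nor does "about 50" describe the response subset, which is unstated and probably smaller, or toxicity, which may use up to 65.

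A reader might also infer that the immune-response objective is affected. Section 12.7.1 sends immune response over time to a mixed model, so it is not, unless a yes/no definition of response is modelled instead.

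The exploratory label and the model-fit fallback also count in the plan's favour. The label reduces the weight of the point. The fallback does not remove it: separation means the estimate does not exist, which is not poor fit, and another link fitted by maximum likelihood can fail in the same way. Finally, exact tests also cope with an empty cell, so Firth is not the only remedy.

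**Conclusion.** The point holds for sparse binary outcomes: chiefly objective response in its unstated subset, and Grade 3-4 toxicity if it turns out to be infrequent. There the named test is uninformative under separation and the plan has no rule for that case. Under the assumed rates and splits, the power given up runs from about 10 points (25 per group, 30% v 10%) to about 50 points (25 per group, 30% v 3%). It is nil at 70% v 30% with 25 per group. These figures illustrate the range and do not predict what this trial will see.

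The consequence is small. The analyses are exploratory, the response and toxicity rates have exact intervals of their own, and neither the primary test nor the sample size depends on them.

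**What to change.** In Section 12.7.1, replace the sentence on Wald tests with one specifying Firth penalised-likelihood logistic regression, with penalised likelihood-ratio tests and profile-likelihood intervals, for these exploratory models. Say explicitly that Wald tests are not to be used on the Firth estimates. Keep the exploratory label.

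The cost is a sentence of text and slightly more analysis work; the statistician should confirm that the software version in use offers the method, since the documents do not say. Estimates are shrunk towards no effect. Results change little when events are frequent. When events are very few, the method does not create information: in the simulated case with about 4 events in 20 patients, Firth power was still only 0.30. Limiting the number of predictors to suit the event count would therefore be a sensible addition.
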